CONFIDENTIAL AND PROPRIETARY

Information provided herein is the property of the University-Hospital of Brescia. Nothing herein is to be reproduced, published, or disclosed to others in any way without the prior expressed written permission of the University-Hospital of Brescia.

Title of Study: Efficacy of guided biofilm therapy in paediatric patient: a randomized clinical trial

Type of Study: Clinical

Protocol No: PROTOCOL # BABYPLAK NP 5675

Sponsor: ASST Spedali Civili di Brescia

Expected study start date: GEN, 2023 (study initiation)

Study Location/Country: Brescia, Italy

Test Products w/ PDM Numbers:

CE marked Medical Device to be used as an adjunct therapy to standard in pediatric patients
(Confidential information).

Study Title: Efficacy of guided biofilm therapy (GBT) in paediatric patient: a randomized clinical trial.

Study sites:
ASST Spedali Civili di Brescia
University of Brescia
Brescia, Italy.

Study Phase: IV.

Name of Medical Device: Plus Powder® and Biofilm Discloser® (EMS Electrical Medical Systems SA, CH 1260-Nyon, Switzerland)

Objective: The objective of the clinical study is to assess the efficacy of disclosing plaque agent and erythritol powder to remove biofilm and plaque in pediatric patient during professional oral hygiene.

Patient Population: 120 pediatric subject, systemically healthy (ASA I e II), male and female (6 – 12 years), with at least 80% of dental formula and with at least 8/12 frontal dental elements.

Structure:
Parallel arms: Number of treatments: 4
- Guided biofilm therapy with disclosing plaque (GBT+)
- Guided biofilm therapy without disclosing plaque (GBT-)
- Ultrasonic debridement with disclosing plaque (US+C+)
- Ultrasonic debridement without disclosing plaque (US+C-)

Duration of study: 36 months.
36 months enrolment

Number of Centers: One.

Method of Patient Selection: pediatric patients who require professional oral hygiene

Total Sample Size: 120 pediatric subjects will be recruited (randomized) to participate in this study, with 120 expected to complete the study.

Primary Efficacy Variable: Primary outcome measure will be the percentage of area in which the disclosing plaque agent is present (RPA: Residual Plaque Area) in all groups after professional oral hygiene

Efficacy of guided biofilm therapy (GBT) in pediatric patient: a randomized clinical trial.

PROTOCOL #BABYPLAK

Protocol Date: OCT 10, 2022

Protocol Approval

Signature Page

Date

Responsibilities

The **principal investigator's** responsibilities are described in detail in ISO norm 14155:2011 for the clinical investigation of medical devices for human subjects.

The role of the principal investigator is to implement and manage the day-to-day conduct of the clinical investigation as well as ensure data integrity and the rights, safety and well-being of the subjects involved in the clinical investigation.

The principal investigator shall be qualified by education, training and experience to assume responsibilities for the proper conduct of the clinical investigation. In particular, the principal investigator is responsible for:

- qualification of investigation site;
- communication with Ethics Committee;
- compliance with Informed Consent process;
- compliance with Clinical Investigation Plan.

Under the direct supervision of the Principal Investigator, certain duties may be delegated during the course of the study. These responsibilities will be documented on the transfer of responsibilities form maintained in the Investigator Site file.

The **Statistician** will be responsible for:

- sample size calculation;
- statistical plan;
- statistical section of the protocol;
- statistical evaluation;
- final statistical report.

OBJECTIVE

The study will be performed to assess the efficacy of disclosing plaque agent (DPA) and erythritol powder to remove biofilm and plaque in pediatric patient during professional oral hygiene.

INTRODUCTION

In the mouth of the patients the biofilm is not always evident, so its removal can be difficult. Using the disclosing plaque agent before the therapy as a guide to remove the biofilm may be a solution. Thanks to this tool, we can clearly see where the plaque is, so its removal can be easier. In pediatric patients is more difficult to remove biofilm and plaque cause of less collaboration to a correct oral hygiene. Probably, using a disclosing plaque agent that guide the operator, could give more security and faster for a better removal of the biofilm. Moreover, the use of low abrasiveness powder could lead to several advantages like a decrease of patients' uncomfortable feeling, the shortest execution time and the possibility of cleaning areas with difficult access and the less damage on soft and hard tissue respect the traditional professional oral hygiene.

For this reasons, we decided to study the efficacy of this method.

STUDY OUTCOMES

Primary outcome measure: comparison between groups of the percentage of area in which the disclosing plaque agent is present (RPA: Residual Plaque Area).

RPA: residual plaque area: percentage of area with residual plaque coloured by disclosing plaque agent. This will be calculated with a ImageJ Software.

Secondary outcome measure:

- comparison between groups of FMPS (Full Mouth Plaque Score) after professional oral hygiene – clinical parameter
- comparison between groups on execution time
- comparison between groups about feeling of patient ad operator

STUDY POPULATION

One hundred and twenty (120) children, aged 6-12 years, will be entered into study (randomized). It is expected that forty (120) subjects will complete the study.

Randomized subjects who deviate from the protocol (major protocol deviation) and, for this reason, are excluded from the analysis, will be replaced to guarantee that the sample required for the analysis (120) is reached.

Patient will be treated at the Department of Surgical Specialities Radiological Science and Public Health, School of Dentistry, Section of Periodontics, Brescia, Italy from 01/2023.

Inclusion Characteristics

- Signed Informed Consent Form (pediatric patient and parent).
- Male and female subjects, aged 6 -12 years, inclusive.
- Good general health (ASA I e II)
- With at least 80% of dental formula
- With at least 8/12 frontal dental elements.

Exclusion Characteristics

- Not willing to follow the agreed protocol.
- Presence of orthodontic appliances.
- Tumors or significant pathology of the soft or hard tissues of the oral cavity.
- Current radiotherapy or chemotherapy.
- History of allergy to Erythritol.
- History of adverse reactions to lactose or fermented milk products.

A written informed consent will be obtained from each included patient after explanation of the risks and benefits of participating to this study. No change in the trial design will be made after approval of the Ethical Committee.

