2. TREATMENTS

Plus Powder and Biofilm Discloser[®] by EMS Electrical Medical Systems SA, CH 1260-Nyon, Switzerland will be delivered to the study center prior study start.

Concomitant Therapy

A necessary concomitant medication or therapy is permitted as long as it is not excluded in the exclusion criteria. Every medication has to be reported in the CRF (Appendix 1) and in the Concomitant Medication form (Appendix 2). All changes during the study are to be reported in the CRF. Usage of prohibited therapy will lead to the exclusion of the subject.

Blinding and Randomization

Blinding: The statistician will be blinded to the 4 groups identification, and defined as all the possible combination of A-b (treatment) and B-b (DPA usage).

Randomization and allocation concealment: The randomization will be done based on a computer-generated table, using a random blocks randomization algorithm, that links each patient to one of the four treatment combinations

Implementation: The Principal Investigator will be informed immediately of Serious Adverse Events (SAEs), regardless of the causality relationship between the administration of the investigational treatment and the SAE.

3. **PROCEDURE**

Screening and Selection of Subjects

Patients visiting the Department of Dentistry at Brescia University will be asked to participate in this study. Subjects will report to the clinical facility and be screened by the dental examiner to identify those subjects who meet the inclusion/exclusion characteristics. The findings of this initial screening procedure will be recorded on the CRF. Subjects who meet the inclusion/exclusion characteristics and sign an Informed Consent Form will be entered into the study.

Baseline Oral Soft and Hard Tissue Assessment

All subjects will receive an evaluation of their oral soft and hard tissues. This examination will include an evaluation of the soft and hard palate, gingival mucosa, buccal mucosa, mucogingival fold areas, tongue, sublingual and submandibular areas and the tonsillar and pharyngeal areas. The results of this evaluation will be recorded on the CRF.

Clinical Periodontal Evaluation

All patients receiving treatment will be evaluated by the dental examiner for the following assessments

- Full Mouth Plaque Score (FMPS).

All parameters will be recorded in the CRF.

Treatment

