5. MONITORING AND AUDIT

Study Monitoring

The study will be monitored by the Principal Investigator at periodic intervals during the course of the study to ensure that the study is being conducted according to Good Clinical Practice.

The Investigators will be contacted by the PI on a regular basis. On this occasion, the progress of the study will be discussed with the Investigator and the CRFs will be checked for completeness and consistency and to verify compliance with the study protocol.

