6. SUBJECT TERMINATION/WITHDRAWAL PROCEDURES

All efforts will be made to determine the reason(s) why a patient is withdrawn from the study. Subjects could be withdrawn from the study if any of the following occur:

1. Subject fails to substantially comply with the protocol requirements;
2. Subject develops a serious adverse reaction. The Study Investigator will immediately notify the PI and information will be recorded on a Serious Adverse Event Form (Appendix 3);
3. Subject elects to terminate participation in the study. Participation in the study is voluntary. A subject has the right to withdraw from the study at any time for any reason.

The Investigator may terminate the study at any time if the risk-benefit ratio is no longer favourable. Before discontinuation, the Investigator should inform the PI and ask for advice. If the Investigator is concerned about continuation of the study, his/her concerns should be transmitted immediately to the PI.

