7. DOCUMENTATION AND DATA MANAGEMENT

Data collection in the case report form (CRF)

All study data will be recorded in the case report forms identified by the subject number. Only the principal investigator, co-investigators, or designated study personnel may make entries in the case report forms.

The Investigator has to identify all data that were directly recorded into the CRF and to be considered to be source data.

The CRFs will be checked for completeness and plausibility by the PI. The Investigator will resolve any queries.

Investigator Site File (ISF)

The ISF includes all documents that are required for the clinical study. During monitoring, the ISF will be checked regularly for completeness and actuality. After the clinical trial is finished or stopped, the ISF has to be stored 15 years in the study center.

Data Management

Data extraction from CRFs into a single, electronic database is performed by examiners. Discrepancies are to be clarified and corrected by authorized persons by means of documented data queries between Statistician and Investigator(s).

After the study is finished and before data are analyzed, a blind data review meeting will be held between the investigator and the statistician. When the database has been declared to be complete and accurate, it will be locked. Any changes to the database after this procedure can only be made by joint written agreement among the clinical trial leader, the trial statistician, and the co-investigators.

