10. ADMINISTRATIVE ASPECTS

Final Report

Following the completion of the study, the PI shall prepare a final study report. The final report will include a general description of the conduct of the study including protocol deviations, subject withdrawals, discussion of any adverse events, safety and efficacy data, and statistical analysis of the data. This report will be shared with the Co-investigator at the Participating Centre by the Principal Investigator, and agreed upon parts before being sent to the Sponsor.

Data Retention

The information in this and any further document contains trade secrets and commercial information that are privileged or confidential and may not be disclosed unless such disclosure is required by law or regulations.

In any event, persons to whom the information is disclosed must be informed that the information is privileged or confidential and may not be further disclosed by them.

The files pertaining to this study will be kept by the University-Hospital of Brescia for a period of 15 years from the day of delivery of the final report and will be available for consultation by competent authorities at any time.

The Investigators will retain originals of the approved study protocol, copies of completed CRFs, subjects' participation agreements, relevant source documents and all other supporting documentation related to the study for a period of 5 years. These files must be made available for inspection upon reasonable request by an authorized representative of EMS or the competent authorities.

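### Randomised children with an undefined major protocol deviation are dropped from the analysis and replaced, and no efficacy analysis of all randomised children is planned

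*Combined protocol and SAP*

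**What the plan says.** The rule is in the Study Population section: "Randomized subjects who deviate from the protocol (major protocol deviation) and, for this reason, are excluded from the analysis, will be replaced", and its purpose is "to guarantee that the sample required for the analysis (120) is reached". The section does not say what makes a deviation major, who decides, or which arm the replacement enters.

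Other sections touch on non-compliance without defining the term:

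- Section 2, Concomitant Therapy: "Usage of prohibited therapy will lead to the exclusion of the subject".
- Section 6 lists as a ground for withdrawal: "Subject fails to substantially comply with the protocol requirements".
- The Responsibilities section makes the principal investigator answerable for "compliance with Clinical Investigation Plan", and under section 5 "the CRFs will be checked for completeness and consistency and to verify compliance with the study protocol".
- Section 10 on the final report: "The final report will include a general description of the conduct of the study including protocol deviations, subject withdrawals".

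Section 4 specifies beta regression for RPA but names no efficacy population. Its only analysis set is the safety set of all treated patients, used for safety summaries. Section 2 describes only the statistician as blinded. Section 7 provides: "After the study is finished and before data are analyzed, a blind data review meeting will be held between the investigator and the statistician".

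**The concern.** Randomisation protects the comparison only if the children analysed are those randomised, or if removals are unrelated to arm and outcome. The rule as written secures neither.

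The treating clinician necessarily knows the arm. At the end of treatment the dye is re-applied, scored and photographed in the same session (section 1). RPA itself is computed from images in ImageJ, but the remaining dye can already be seen. A judgement that a deviation was major could thus be made by someone who knows the arm and has a good idea of the result.

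If that happened, the technique-by-dye interaction, which is the parameter on which the trial is sized, could be biased in either direction. No planned analysis would show by how much, because the excluded children's RPA would appear in no efficacy result.

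**Working it through.** **1. Can other text fill the gap?** Set side by side, the passages do not supply a rule. The prohibited-therapy and withdrawal clauses concern participation in the study; neither mentions the analysis or uses the term major deviation. The compliance duties are general and do not assign the decision to exclude. The blind data review takes place after the study is finished, whereas replacing children presupposes that exclusions are decided while enrolment is open. The review is not given this task, and it includes the investigator, who is not described as blinded.

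**2. Inputs for the illustration.** All are from section 4: RPA 10% without dye in both techniques, 2.9% for ultrasonic with dye (US+C+), 1.5% for GBT+, phi = 55, 30 per arm, 5% significance level. Assumed: a two-sided Wald test, logit link and common phi. The documents give no deviation rate, so the number replaced is also an assumption.

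**3. Reproducing the plan's power.** The interaction on the logit scale is
[logit(0.015) − logit(0.10)] − [logit(0.029) − logit(0.10)] = logit(0.015) − logit(0.029) = −4.185 + 3.511 = −0.674.
Simulated power is 84.9% (20,000 runs) against the stated 83%. The plan used 1,000 runs, so its Monte Carlo standard error is √(0.83 × 0.17 / 1000) = 1.2 points. The gap of 1.9 points is about 1.6 standard errors, so the plan's figure is reproduced.

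**4. Effect of selective replacement.** For false positives, both dye arms are set to 2.9% (no interaction) and children are removed from GBT+. For power, the planned means are kept and children are removed from US+C+. Each replacement is a fresh draw in the same arm. There were 20,000 runs per cell.

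| Children replaced, of 30 in one arm | 0 | 1 | 3 | 5 |
|---|---|---|---|---|
| Drawn at random from the upper half of RPA: false positives, % | 5.7 | 5.4 | 5.9 | 7.2 |
| Drawn at random from the upper half of RPA: power, % | 84.9 | 83.6 | 79.4 | 74.8 |
| Highest RPA values (extreme case): false positives, % | 5.7 | 6.1 | 9.0 | 11.8 |
| Highest RPA values (extreme case): power, % | 84.9 | 82.5 | 75.6 | 69.3 |

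The 5.7% baseline is the Wald test's own excess over 5%. Its Monte Carlo standard error is √(0.057 × 0.943 / 20,000) = 0.16 points, so the upper-half results for 1 and 3 children (5.4% and 5.9%) do not differ detectably from baseline. With 5 children replaced and no true interaction, the estimate shifts by −0.087 (upper half) or −0.144 (extreme), which is 13% or 21% of the planned effect (0.087/0.674 and 0.144/0.674).

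**5. When there is no bias.** If exclusions are random, false positives are 5.3% (3 replaced) and 5.4% (5 replaced), and power with 5 replaced is 85.3%. If the same number of highest-RPA children leave both dye arms, the shift is 0.

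**6. Sensitivity to the replacement's arm.** If replacements are allocated at random to any arm, the extreme case for 1, 3 or 5 children gives false positives of 6.2%, 8.5% or 12.7% and power of 82.1%, 74.2% or 65.0%. The picture is much the same.

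**The case against.** The strongest reply is that little is likely to happen. Treatment and outcome share one visit, all 120 children are expected to complete, and children unwilling to follow the protocol are excluded at entry. One exclusion hardly matters; larger effects need 3 to 5 of 30 children (10% to 17%) removed from a single arm in an outcome-related way. This stands, and it limits the weight of the point.

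The extreme case also fits the rule poorly. Picking the highest values in an arm needs the complete arm and the ImageJ results, while replacement under rolling admission happens earlier and the clinician sees only remaining dye. This stands too, so the upper-half figures are the better guide and the extreme case is an outer bound.

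The plan is not silent on oversight. Deviations go into the final report, eligibility departures need pre-authorisation and documentation (section 9), and safety tables by group on all treated children would let a reader work out how many treated children per arm were left out. That would reveal an imbalance in numbers but not its effect on RPA.

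Two stronger readings are tempting. A reader might infer that exclusions will be selective, or that the result will be biased; the documents give no deviation rate and nothing to show this. A reader might also infer from the Introduction, which expects the powder to shorten treatment and reduce discomfort, that unfinished sessions would be commoner with ultrasonic treatment and would be excluded. The documents do not class an unfinished session as a major deviation and give no rates, so this cannot be quantified from them.

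**Conclusion.** The point holds as a weakness in a stated rule that should be corrected, not as evidence of bias. The plan removes and replaces randomised children on an undefined criterion, with no safeguard tied to that decision and no all-randomised efficacy analysis against which to check it.

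The likely size is small. With moderate selection in one arm, false positives stay at or near baseline for 1 to 3 children and reach about 7% at 5, while power falls from about 85% to between 84% and 75%. The outer bound at 5 children is about 12% false positives and 69% power. These figures rest on the plan's beta model, same-arm replacement and assumed numbers of exclusions. The sample-size calculation itself is not in dispute.

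**What to change.** 1. Make the primary analysis all randomised children with an RPA photograph, in the arm assigned, regardless of deviations.
2. Define major protocol deviation before enrolment, name who applies it, and have it applied without knowledge of arm or RPA. Use it only for a per-protocol sensitivity analysis.
3. Replacements may be enrolled, but they must not displace excluded children from the primary analysis.
4. State in advance how children without a photograph are handled, with a sensitivity analysis, and specify how data from sessions that ended early are treated. Item 1 cannot remove bias from missing photographs, so an assumption remains here.
5. Extend the section 10 report to give exclusions and reasons by arm.

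The cost is protocol and SAP wording plus one or two extra analyses. Power may fall if deviating children have higher RPA. If such children end at 10% in both dye arms (an assumption), simulated power is about 82% with one of 30 per dye arm and 76% with three, against 85% with none. The stated 83% should therefore be described as assuming complete, adherent sessions. Section 9 requires the ethics committee to be notified of changes and to approve substantial ones in writing, and the Study Population section rules out design changes after approval, so an amendment may be needed.

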1. STUDY DESIGN

The study design was chosen according to the current standards required by GCP and according to national requirements.

- a. A 2 by 2 parallel design.
- b. The RCT will be run as mono-center;
- c. A total of 120 subjects will be recruited to participate in the study. It is expected that all of 120 subjects will complete the study in total;
- d. Admission into the study will be via rolling admission (estimated recruitment time: 36 months);
- e. Each subject must be pediatric patient who needs a professional oral hygiene;
- a. Each subject will follow the following treatment protocol:
 - i. - Visit (T0): consent secured; screening and entry into study; baseline data collection (FMPS), randomization into one of the four treatment arms as per the randomization protocol;

ii. - Treatment (T0): all patients will receive a full-mouth professional oral hygiene. Procedures will be performed in the following chronological sequence:

- A. Place Optragate
- B. Start the timer for the executive time
- C. According to the randomization list, patients assigned to the **GBT+** will do professional oral hygiene guided by disclosing plaque (GBT):

- Placement the disclosing plaque agent (Biofilm Discloser® (EMS Electrical Medical Systems SA, CH 1260-Nyon, Switzerland)) on the teeth and rinse with only water;
- Tissue decontamination with Air-flow (Air-flow® Prophylaxis Master EMS, Nyon Switzerland) and erythritol powder (PLUS powder® EMS, Nyon Switzerland);
- Supragingival removal biofilm with Air-flow (Air-flow® Prophylaxis Master EMS, Nyon Switzerland) and erythritol powder (PLUS powder® EMS, Nyon Switzerland);
- Subgingival removal biofilm with Air-flow (Air-flow® Prophylaxis Master EMS, Nyon Switzerland) and erythritol powder (PLUS powder® EMS, Nyon Switzerland);
- Calculus removal with piezoceramic device (Air-flow® Prophylaxis Master EMS, Nyon Switzerland), with a slim tip (PS® EMS, Nyon Switzerland);
- The treatment ends, when all the disclosing plaque has been removed;
- Stop the timer and note the executive time;
- Questionnaire patient and operator;
- Placement of the disclosing plaque agent (Biofilm Discloser® (EMS Electrical Medical Systems SA, CH 1260-Nyon, Switzerland)) on the teeth and rinse with only water;
- Note the FMPS;
- Collection of the pictures.

D. According to the randomization list, patients assigned to the **GBT-** will receive professional oral hygiene without the guide by disclosing plaque. The treatment as same as group A without the use of disclosing plaque at the beginning.

E. According to the randomization list, patients assigned to the **US+C+** will do traditional professional oral hygiene guided by disclosing plaque:

- Placement the disclosing plaque agent (Biofilm Discloser® (EMS Electrical Medical Systems SA, CH 1260-Nyon, Switzerland)) on the teeth and rinse with only water;
- Calculus removal with piezoceramic device (Air-flow® Prophylaxis Master EMS, Nyon Switzerland), with a slim tip (PS® EMS, Nyon Switzerland);
- Supragingival and subgingival removal biofilm with rubber cup and polish;

- The treatment ends, when all the disclosing plaque has been removed;
- Stop the timer and note the executive time;
- Questionnaire for the patient and the operator;
- Placement of the disclosing plaque agent (Biofilm Discloser[®] (EMS Electrical Medical Systems SA, CH 1260-Nyon, Switzerland)) on the teeth and rinse with only water;
- Note the FMPS;
- Collection of the pictures.

- F. According to the randomization list, patients assigned to the **US+C-** will receive professional oral hygiene without the guide by disclosing plaque. The treatment as same as group C without the use of disclosing plaque at the beginning.
- G. All treatments are made by the same clinician.
- H. Data collection (FMPS): A PCP-UNC 15 periodontal probe is used on six sites per tooth (mesio-buccal, buccal, disto-buccal, mesio-lingual, lingual and disto-lingual) with a gentle probing force by the same clinician. Measurements are rounded to the nearest millimeter.
- I. Clinical assessment data will be recorded via hard copy CRFs. CRFs will be submitted to a data entry staff member for entry into the statistical database. At the conclusion of the study, such statistical database will be submitted to the statistician for the preparation of the statistical analysis and the final study report.

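### As written, FMPS is probed on the freshly dyed teeth before the pictures for the primary outcome (RPA) are taken; the pictures should come first.

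*Combined protocol and SAP*

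**What the plan says.** Section 1 (Study Design), under Treatment (T0), introduces the steps with "Procedures will be performed in the following chronological sequence", so the order of the lists is binding. The GBT+ list (item C) and the US+C+ list (item E) end alike. After the timer stops and the questionnaires are done, the steps are:

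1. "Placement of the disclosing plaque agent (Biofilm Discloser® (EMS Electrical Medical Systems SA, CH 1260-Nyon, Switzerland)) on the teeth and rinse with only water"
2. The FMPS is noted.
3. "Collection of the pictures"

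GBT- (item D) and US+C- (item F) follow the same lists by reference and omit only the dye at the start. No list re-applies dye between the FMPS and the pictures.

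Item H, on collection of FMPS data, reads "A PCP-UNC 15 periodontal probe is used on six sites per tooth", to be done "with a gentle probing force by the same clinician". It adds "Measurements are rounded to the nearest millimeter".

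Study Outcomes defines the primary outcome, RPA, as "percentage of area with residual plaque coloured by disclosing plaque agent", and says "This will be calculated with a ImageJ Software". FMPS after treatment is a secondary outcome.

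**The concern.** RPA is a measure of dyed area, and the closing pictures are the only images the protocol mentions. They are therefore its evident source, although no sentence says so. If item H applies to the final FMPS, every tooth is touched with a probe at six sites after the last staining and before the picture. Contact could lift dyed plaque or smear it. Any bleeding could add colour, and the interval gives the dye time to fade or dilute. The documents report none of these effects, but the order leaves the primary outcome open to them for the sake of a secondary one.

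The plan's expected values make this worth attention. Section 4 (Statistical Analysis) assumes RPA of only 2.9% and 1.5% in the two guided arms. The parameter of interest is the interaction of technique with disclosing agent, which on the logit scale depends on the ratio of those two small values. A change of a few tenths of a percentage point is not negligible against them.

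**Working it through.** **Inputs.** From section 4, sample size determination: beta regression; phi = 55; mean RPA 10% in both arms without initial dye, 2.9% in US+C+ and 1.5% in GBT+; 30 children per arm; 5% significance; stated power 83%. Two assumptions are added: a logit link and a two-sided test. The plan does not state sidedness, but a one-sided 5% test would give about 91%, so the stated figure fits a two-sided one.

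**The plan's own figure.** The interaction is

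[logit(GBT+) - logit(GBT-)] - [logit(US+C+) - logit(US+C-)].

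Both arms without initial dye are at 10% and cancel, leaving

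logit(0.015) - logit(0.029) = -4.185 + 3.511 = -0.674.

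For each arm the variance of the estimated logit is about 1 / {n phi² [ψ'(μ phi) + ψ'((1-μ) phi)] μ²(1-μ)²}, where ψ' is the trigamma function. This gives 0.0062 for each 10% arm, 0.0158 for US+C+ and 0.0228 for GBT+. The sum is 0.0510 and its square root 0.226. Allowing for estimation of phi, the standard error is 0.227. Power is Φ(0.674/0.227 - 1.96) = Φ(1.01), or 84.3%. Simulation gave 84% to 85%. A 1000-run simulation such as the plan's has a standard error of about 1.2 points, so the stated 83% is reproduced.

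**How much contact.** At six sites per tooth, the 8 to 12 frontal teeth that the inclusion criteria imply carry 48 to 72 probe sites. Three of the six sites on each tooth are buccal, which makes 24 to 36. The documents do not name the photographed surfaces, so the number of contacts that fall inside the pictures is unknown.

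**What a disturbance could do.** The documents give no artefact size. The changes below are assumptions, applied equally to the mean of every arm. The arms without initial dye remain equal to each other and still cancel, so interaction = logit(GBT+) - logit(US+C+).

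| Assumed change in every arm | US+C+ | GBT+ | Interaction |
|---|---|---|---|
| None | 2.9% | 1.5% | -0.674 |
| Half of the dyed area lost | 1.45% | 0.75% | -0.666 |
| 0.25 points added | 3.15% | 1.75% | -0.602 |
| 0.5 points added | 3.4% | 2.0% | -0.545 |
| 1.0 point added | 3.9% | 2.5% | -0.459 |
| 0.25 points removed | 2.65% | 1.25% | -0.766 |
| 0.5 points removed | 2.4% | 1.0% | -0.890 |
| 1.0 point removed | 1.9% | 0.5% | -1.349 |

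For example, with 0.5 points added, logit(0.020) - logit(0.034) = -3.892 + 3.347 = -0.545. With 0.5 points removed, logit(0.010) - logit(0.024) = -4.595 + 3.705 = -0.890.

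The three mechanisms thus give three answers. Equal proportional loss leaves the interaction almost where it was (simulated power 84% to 86% for losses of 10% to 50%) but lowers every reported RPA by the lost fraction. Added area pulls the interaction towards zero. Removed area pushes it away from zero.

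**The case against.** The strongest reply is that item H may not govern the final score. It does not say whether it covers the baseline FMPS, the final FMPS or both, and section 1 uses the term data collection for the baseline FMPS at the T0 visit. The final FMPS is noted on teeth just re-dyed, when plaque can be scored by eye. Rounding to the millimetre fits a depth reading, not a plaque score, so item H may not describe FMPS scoring at all. This doubt stands. It limits the point to the protocol as written, where probing at both scorings is the natural reading. It also shows that the text needs clarifying.

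Nor does any passage say that gentle probing alters dyed plaque, that it makes gums bleed, or that the image analysis would count blood as dye. That stands too, so the wording here is that probing can disturb the surfaces.

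A reader might go further and infer that the order costs the trial power or biases the comparison between arms. The documents support neither inference. A loss of power follows only if colour is added; removed dye gives no change or a larger interaction. The order is the same in all four arms, so no bias between arms is shown. Dye loss that differs by arm cannot be excluded, because one clinician gives all treatments, item H has the probing done by the same clinician, and section 2 states blinding only for the statistician. In simulation, an assumed 10% loss in US+C+ alone cut the rejection rate to 77%, and a 20% loss in GBT+ alone raised it to 96%. Nothing in the documents indicates that either occurs.

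**Conclusion.** The point holds as a matter of sequence. As written, a contact examination for a secondary outcome stands between the final staining and the pictures that evidently supply the primary outcome, in every arm and with no re-dyeing. Confidence in this is high. It rests on two readings: that the closing pictures are the source of RPA, and that item H covers the final FMPS.

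That the probing changes RPA is plausible but not documented; confidence there is moderate at most. Size and direction are unknown. At an assumed 0.5 points the interaction could lie anywhere from about -0.55 to about -0.89 against a planned -0.67, depending only on whether area is added or removed. The sample size and the stated power need no revision. The reason to act is that the exposure of the primary outcome is avoidable at almost no cost.

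**What to change.** In the GBT+ and US+C+ lists of section 1, and so by reference in GBT- and US+C-, exchange the last two steps: apply the final dye and rinse, take the pictures immediately, then note the FMPS. In item H, state which FMPS scorings it covers, whether the final one involves contact, and what the millimetre rounding refers to. If the final FMPS is in fact scored by eye, saying so removes most of the concern, though taking the pictures first still costs nothing in conduct.

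The price is a slightly later FMPS reading and a minor protocol amendment. Section 9 requires prior approval for changes, and Study Population rules out design changes after ethics approval, so the amendment should present this as a reordering of two measurements within the same visit. Treatment, staff, materials and sample size stay as they are.
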